# 2.0 STUDY OBJECTIVES

#### 2.1 Primary Objectives

**2.1.1** To predict kidney mass diagnosis using 3D CEUS generated metrics (see Section 7.2.1).

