#### 2.3 Endpoints

The primary study endpoint will be 3D CEUS generated metric(s) that best predict kidney mass diagnosis based on pathologic examination.

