# 7.0 STATISTICAL CONSIDERATIONS

#### 7.1 Sample Size and Accrual

We will enroll 25 adult subjects with suspected with suspected kidney cancer and planned surgical nephrectomy. We have deep recruitment experience for kidney CEUS imaging. Approximately 150 nephrectomies for localized disease are performed at UNC yearly. Based on our previous recruitment rate of ~75% and a strong partnership with our urology colleagues, we anticipate no problems meeting our recruitment goal of 25 subjects.

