#### 7.1.1 Primary Objective

# 7.1.1.1 Predicting kidney mass diagnosis using 3D CEUS generated metrics.

The proposed sample of 25, assuming 60% clear cell legions, achieves 63.2% power to detect a difference of 0.1000 between a diagnostic test with an area under the ROC curve (AUC) of 0.8000 and another diagnostic test with an AUC of 0.9000 using a two-sided z-test at a significance level of 0.050. The correlation between the two diagnostic tests is assumed to be 0.9 for the positive group and 0.9 for the negative group.

The proposed sample of 25, assuming 60% clear cell legions, achieves 88.7% power to detect a difference of 0.1500 between a diagnostic test with an area under the ROC curve (AUC) of 0.8000 and another diagnostic test with an AUC of 0.9500 using a two-sided z-test at a significance level of 0.050. The correlation between the two diagnostic tests is assumed to be 0.9 for the positive group and 0.9 for the negative group.

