standard of histologic diagnosis to differentiate clear cell from non-clear cell tumors, we will use logistic regression to build predictive models based on multiple parameters from CEUS (WI, WO, MTT, TTP, PE and tumor volume), B-mode US images (length, echogenicity, shape), as well as patient factors (age, sex, race) (Table 1). We will assess the effects of individual parameters using hypothesis tests based on parameter estimates from the fitted logistic regression model. This approach facilitates assessment of the added value of the CEUS measurements over other patient factors. We will calculate nonparametric estimates and 95% confidence intervals for area under the curve (AUC) using the fitted logistic regression models, both with and without non-CEUS patient factors. We will use model selection procedures, including AUC, to identify a final model, with a one-sided test of AUC  $\leq .8$  vs AUC  $\geq .8$  at alpha=.05 for the final model. We will use model selection procedures based on optimizing AUC to identify a final model, with a one-sided test of AUC<=0.8 vs AUC>=.8 at alpha=.05 for the final model.

Gold Standard Comparator: Histologic diagnosis from pathologic tissue.

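### Section 7.2.1 sets out to show what CEUS adds, but specifies no model without CEUS, and its test of AUC against 0.8 does not require any CEUS term

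*Combined protocol and SAP*

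**What the plan says.** The primary objective (section 2.1) is "To predict kidney mass diagnosis using 3D CEUS generated metrics". The endpoint (section 2.3) is the "3D CEUS generated metric(s) that best predict kidney mass diagnosis".

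Section 7.2.1 and its Table 1 list 12 candidate predictors of clear cell versus non-clear cell histology:

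- six from CEUS: WI, WO, MTT, TTP, PE and tumour volume;
- three from B-mode: length, echogenicity and shape;
- three patient factors: age, sex and race.

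The section then describes four steps, in this order:

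1. Single parameters are tested from the fitted logistic model, followed by the statement "This approach facilitates assessment of the added value of the CEUS measurements over other patient factors".
2. AUCs with 95% confidence intervals are estimated "using the fitted logistic regression models, both with and without non-CEUS patient factors".
3. A final model is chosen by procedures that optimise AUC.
4. That model is tested one-sided at 0.05 against an AUC of 0.8.

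Section 7.2.2 reuses this strategy for bolus and infusion imaging.

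**The concern.** To measure what CEUS adds, one of the two models compared must leave CEUS out. In step 2 CEUS is in both models and the patient factors are switched on and off, so the difference answers the reverse question. The text is also unclear about B-mode. Table 1 lists B-mode factors apart from patient factors, so B-mode may stay in both models. CEUS is then isolated even less, and no CEUS-only AUC is computed.

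Step 4 adds to this. Half of the candidates are not CEUS metrics, and no rule keeps a CEUS term in the final model. A model driven by B-mode and patient factors can pass the 0.8 test, while the objective and endpoint are about CEUS. At stake is whether a favourable primary result could be attributed to CEUS.

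**Working it through.** **Inputs.** Section 7.1: "We will enroll 25 adult subjects". Section 7.1.1.1: 60% clear cell, so 0.60 × 25 = 15 clear cell and 10 non-clear cell; correlation 0.9 between the two tests in each group; "using a two-sided z-test at a significance level of 0.050". Section 7.2.1: 6 CEUS and 6 non-CEUS candidates.

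**Step 1: the plan's own power figures.** "The proposed sample of 25, assuming 60% clear cell legions, achieves 63.2% power to detect a difference of 0.1000" (0.80 vs 0.90), and it "achieves 88.7% power to detect a difference of 0.1500" (0.80 vs 0.95). I used the Obuchowski-McClish binormal variance with equal spread in both groups:

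- a = √2·Φ⁻¹(AUC), f = exp(−a²/4)/√(4π), g = −a·exp(−a²/4)/√(16π), R = 10/15.
- Cov(r) = [f₁f₂(r + r/R + r²a₁a₂/2) + g₁g₂r²(1+R)/(2R) + r²(f₁g₂a₁ + f₂g₁a₂)/2] / 15. The variance is the same expression with equal AUCs and r = 1.
- Power = Φ((d − 1.96·SE₀)/SE₁), where SE₀ takes both AUCs as 0.80.

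SE₀ = √(2 × (0.00769 − 0.00682)) ≈ 0.0418.

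- 0.80 vs 0.90: SE₁ = √(0.00769 + 0.00362 − 2 × 0.00458) ≈ 0.0464. Power = Φ((0.10 − 0.0819)/0.0464) = Φ(0.39) ≈ 65.2%; the plan states 63.2%.
- 0.80 vs 0.95: SE₁ = √(0.00769 + 0.00149 − 2 × 0.00284) ≈ 0.0591. Power = Φ((0.15 − 0.0819)/0.0591) = Φ(1.15) ≈ 87.5%; the plan states 88.7%.

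Both agree within about 2 points. The primary power statement therefore concerns two correlated AUCs, whereas 7.2.1 tests one AUC against a fixed 0.8 and names no second score.

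**Step 2: what the planned contrast estimates.**

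| Comparison | Estimates | In 7.2.1? |
|---|---|---|
| (CEUS + patient factors) − (same model without patient factors) | what patient factors add to CEUS | yes |
| (CEUS + non-CEUS) − (non-CEUS only) | what CEUS adds | no |

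**Step 3: can the 0.8 test be passed when CEUS is uninformative?** Simulation assumptions: 15 vs 10 subjects, 12 independent normal predictors, six CEUS metrics of pure noise, in-sample AUC, DeLong variance, and pass if (AUC − 0.8)/SE > 1.645.

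First, a non-CEUS score fixed in advance, so that nothing is overfitted (4,000 runs). With true AUC 0.80 / 0.85 / 0.90 / 0.95 it passes in 12% / 27% / 52% / 86% of trials. The 12% at the boundary, against a nominal 5%, shows that the approximation is poor at this sample size.

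Second, fitted models, by true joint AUC of the non-CEUS factors:

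| | 0.5 | 0.7 | 0.8 |
|---|---|---|---|
| Forward selection by AUC, at most 3 terms: passes | 16-18% | 26% | 48-53% |
| The same, passes with no CEUS term | 1% | 3% | 10-17% |
| All 12 terms, no selection: passes | 70% | 82-84% | 92-94% |
| All 12 terms: data separated | 55-58% | 69-74% | 84-87% |

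Ranges span independent repeats. Forward selection is costly to simulate: with 150 runs, a rate of 26% has standard error √(0.26 × 0.74/150) ≈ 3.6 points, so these figures are approximate.

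**Step 4: do the single-parameter tests fill the gap?** They adjust each CEUS term for the others, but they do not test the six CEUS terms together and do not enter the 0.8 decision. Run on all 12 terms, about 56% of pure-noise datasets are separated, and more when the non-CEUS factors are informative. Finite maximum-likelihood estimates do not then exist, and Wald tests say nothing. Six-term CEUS-only fits separate in only about 1% of runs.

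**The case against.** The added-value sentence follows directly after the single-parameter tests, so the plan may offer those tests, and not the AUC contrast, as its measure of CEUS value. That is a fair reading. It also does not say that the tests come from the 12-term model. A reader might infer that the Wald tests are unusable in general; breakdown is shown only for the full 12-term fit.

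A reader might also take the 70-94% pass rates as the effect of this defect. They are not. With all 12 predictors noise, the unselected fit already passes in 70% of trials, so most of the figure is in-sample overfitting. The plan, moreover, tests a selected model. The three-term figures are closer to the text, though the three-term cap is itself an assumption.

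Nor does a large with-minus-without difference show CEUS being falsely credited. With noise CEUS and a non-CEUS AUC of 0.7 or 0.8, it averages about 0.967 − 0.79 = 0.18 or 0.983 − 0.78 = 0.20. In those scenarios the non-CEUS factors do have value, and they are what the difference measures.

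Finally, the objective and endpoint speak of prediction, not incremental value, and no section makes the 0.8 test a criterion of trial success. AUCs with intervals are reported either way.

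What remains is that no CEUS-free model is specified, the AUC contrast does not address the stated purpose, and the 0.8 test carries no condition on CEUS.

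**Conclusion.** The point holds in this limited form and should be fixed. From the text alone, without simulation, the planned AUC contrast cannot show what CEUS adds, and passing the 0.8 test is not by itself evidence for the primary objective.

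The size depends on how informative the B-mode and patient factors are, which the documents do not give. Under the assumed three-term selection with uninformative CEUS, the test passes in roughly one trial in six to one in two as the true non-CEUS AUC goes from 0.5 to 0.8. It passes with no CEUS term in about 1% to 10-17%. These rates rest on independent normal predictors, in-sample AUC, DeLong variance and the assumed cap, and they still contain some overfitting.

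A reader might conclude that the study is set up to declare CEUS successful whatever the data show. The documents do not support that: they define no such success rule and do not say that the full 12-term fit is the final model.

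**What to change.** In section 7.2.1:

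1. Specify a non-CEUS-only model (B-mode length, echogenicity and shape, plus age, sex and race), built by the same selection procedure as the full model.
2. As the measure of CEUS added value, report the paired, optimism-corrected AUC difference, CEUS + non-CEUS minus non-CEUS only. Give a 95% interval from a bootstrap that resamples subjects and repeats the model selection in every resample.
3. State explicitly that a CEUS-only score is fitted (six CEUS factors, no B-mode or patient factors). Report its optimism-corrected AUC against 0.8 beside the final-model test. The correction is needed here too: pure-noise CEUS-only scores average an apparent AUC of about 0.79 and pass the uncorrected test in about 7-9% of trials.
4. Say that any claim about CEUS rests on items 2 and 3, and whether B-mode counts among the non-CEUS patient factors.

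**Cost.** One or two extra models on data already collected. The interval will be wide and the headline may be less favourable. By the formula in the working, a paired comparison of 0.80 vs 0.90 has power of about 65% if the two scores correlate 0.9, falling to about 40%, 28% and 17% at assumed correlations of 0.8, 0.7 and 0.5. For 0.80 vs 0.95 the figures are about 88%, 70%, 56% and 36%. The difference should therefore be presented as an estimate with its interval, not as a powered test.

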With bolus administration of undiluted microbubbles, CEUS quantifies measurements like peak intensity, time to peak intensity, and wash-in/wash-out rates from the time intensity curve (TIC), each of which may be used to predict mass subtype. Alternatively, infusion of diluted microbubbles facilitates longer imaging times and uses faster frame rates. Longer imaging time allows for imaging in multiple planes which can capture multiple masses or different planes in a single mass, providing richer information. Faster frame rates can capture rapid wash-in rates with greater granularity than bolus dosing. However, the infusion method TIC does not quantify a wash-out rate, eliminating one metric that may contribute to subtype classification accuracy. Existing data suggest that bolus dosing 2D CEUS has comparable accuracy for malignancy detection compared to contrast-enhanced CT and MRI[17]. The accuracy of infusion dosing is unknown. We will adapt both approaches to generate 3D CEUS images.

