#### 7.2 Data Analysis Plans

#### 7.2.1 Predicting kidney mass diagnosis using 3D CEUS generated metrics.

*Image Analysis (Low MI TIC analysis):* We will use Matlab (Mathworks, Natick, MA) for time intensity curve (TIC) analysis and 3D volume rendering. For each imaging plane, we will create a region of interest (ROI) by delineating the entire mass in the image slice. We will produce a TIC by taking the mean signal intensity in the ROI at each time point and calculate the metrics of wash-in rate (WI), wash-out rate (WO), mean transit time (MTT), time to peak (TTP) and peak enhancement relative to the surrounding parenchyma (PE) for each x-sweep position. A weighted average based on the ROI area at each position will be used to produce single values for the 3D volume for each TIC metric (WI, WO, MTT, TTP and PE). We will repeat this process for each plane of imaging.

3D volume rendering: We will also create 3D renderings of the tumor vasculature from the CEUS images. We will sort the image data collected over the 3-minute period after a bolus injection by the x- (or y-) sweep position, then by capture time in relation to the start of bolus injection through the wash-out period. We will produce a cumulative contrast image (CCI) at each position with the time-dependent image data by summing all time-dependent image data at each position. The images show where the microbubbles have travelled throughout the acquisition period, and since microbubbles are confined to the vascular spaces, the images provide excellent delineation of the vasculature. We will stack the CCIs together to create a 3D rendering.

Multiparametric score and statistical analysis: We will combine the

Table 1. Factors to be used in multiparametric score					
CEUS factors	B-mode factors	Patient factors			
WI, WO, MTT,	Length,	Age, sex, race			
TTP, PE, total	echogenicity,				
volume	shape				

quantitative data derived from CEUS image analyses into a single score. For the primary analysis using the gold

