# 7.2.2 Comparing diagnostic accuracy of F-R infusion imaging technique to low MI bolus imaging technique.

Image Analysis (Flash-Replenishment TIC analysis): For each 0.5-1 cm step, we will produce a TIC by delineating an ROI of the entire mass and measuring the mean contrast signal intensity over the time course of the F-R. We will model TIC using a mono-exponential equation, UI=A(1 -  $e^{-\beta t}$ ), where UI is ultrasound intensity and  $\beta$ , the slope of the tangent to the curve, represents the rate of perfusion. The height of the curve, A, represents the perfusion volume. To produce a single value for  $\beta$  for the entire tumor volume, we will calculate a weighted average based on the ROI area of the mass at each step. This value will serve as the WI rate.

Gold Standard Comparator: Histologic diagnosis from pathologic tissue.

*Statistical Analysis:* We will follow the model building and evaluation strategy used for the primary objective. This will be done separately for bolus and infusion imaging modalities, as well as combining the two multiparametric scores. We will compare AUCs from final logistic regression models obtained for bolus and infusion using a Z-test at alpha=0.05, with standard errors obtained by bootstrapping correctly adjusting for the fact that the two AUCs are calculated using the same data and hence correlated. We will conduct similar tests comparing the AUC based on the combined model to those based on bolus and infusion multiparametric scores separately. The proposed tests with sample size 25 have 80% power to detect a difference of .1 in the AUCs (0.8 vs 0.9) and 90% power to detect a difference of 0.15 (0.8 vs 0.95).

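### The primary test of AUC above 0.8 uses the apparent AUC of a model selected from 12 candidates in the same 25 patients, so its 5% level is not assured

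*Combined protocol and SAP*

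**What the plan says.** Section 7.2.1 combines "quantitative data derived from CEUS image analyses into a single score" and, for the primary analysis of clear cell against non-clear cell histology, fits logistic models on "multiple parameters from CEUS (WI, WO, MTT, TTP, PE and tumor volume), B-mode US images (length, echogenicity, shape") together with age, sex and race. That is 6 CEUS, 3 B-mode and 3 patient factors, 12 candidates in all.

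On estimation it says: "We will calculate nonparametric estimates and 95% confidence intervals for area under the curve (AUC) using the fitted logistic regression models". On selection it speaks twice, in consecutive sentences that are not identical: "We will use model selection procedures, including AUC, to identify a final model", and then "We will use model selection procedures based on optimizing AUC to identify a final model, with a one-sided test of AUC<=0.8 vs AUC>=.8". Both attach a one-sided test at alpha 0.05 to the final model.

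Sections 7.1 and 7.1.1.1 give 25 subjects and assume 60% clear cell lesions. Section 7.2.2 adds: "We will follow the model building and evaluation strategy used for the primary objective", separately for bolus and infusion and for the two combined. The only resampling in the plan is the bootstrap in Section 7.2.2, which supplies standard errors for comparing correlated AUCs.

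**The concern.** The quantity used to choose the model is the quantity then tested, and both steps use the same patients. An AUC computed from a model in the data that selected and fitted it is optimistic: it contains the fit to chance patterns as well as any real discrimination. A test that treats it as the AUC of a fixed marker can reject more often than its nominal 5%. The bootstrap in Section 7.2.2 does not cure this, because a standard error describes spread and leaves the upward bias in place.

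This test is the only formal criterion for the primary objective. If it rejects too often at the boundary, a claim that the CEUS model exceeds 0.8 may owe part of its strength to overfitting. The same optimism carries into the AUC comparisons of Section 7.2.2.

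**Working it through.** **1. Inputs.** 25 patients at 60% clear cell: 0.60 × 25 = 15 clear cell, 10 other (Section 7.1.1.1). Candidates: 6 + 3 + 3 = 12 (Section 7.2.1, Table 1), with more coefficients if race, echogenicity or shape has over two levels. Null AUC 0.8, one-sided 0.05 (Section 7.2.1). The plan names no standard error, selection algorithm or maximum model size for this test, so these were varied.

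**2. The plan's own power figures.** Section 7.1.1.1 gives 63.2% (0.80 vs 0.90) and 88.7% (0.80 vs 0.95) for a two-sided comparison of two tests correlated at 0.9. Take the Obuchowski SEs for 15/10 (0.0974 at 0.80, 0.0727 at 0.90, 0.0493 at 0.95) and a correlation of 0.9 between the AUC estimates:

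- SE of the difference under the null: √(2 × 0.0974² × 0.1) = 0.0436.
- Under 0.90: √(0.0974² + 0.0727² − 2 × 0.9 × 0.0974 × 0.0727) = 0.0451. Power = Φ[(0.10 − 1.96 × 0.0436)/0.0451] = 62.7%.
- Under 0.95, by the same steps: 87.0%.

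Both are within 2 points of the stated values. They describe a paired comparison of two tests and say nothing about the one-sample, one-sided test in Section 7.2.1.

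**3. Cutoff for the planned test.** The Hanley-McNeil variance at A = 0.8 is [A(1−A) + (n₁−1)(q₁−A²) + (n₀−1)(q₂−A²)]/(n₁n₀), with q₁ = A/(2−A) = 0.6667 and q₂ = 2A²/(1+A) = 0.7111.

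- Clear cell positive (n₁ = 15, n₀ = 10): [0.16 + 14 × 0.0267 + 9 × 0.0711]/150 = 0.00782; SE 0.0884; cutoff 0.8 + 1.645 × 0.0884 = 0.945.
- Groups swapped: [0.16 + 9 × 0.0267 + 14 × 0.0711]/150 = 0.00930; SE 0.0965; cutoff 0.959.

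**4. False rejection of the apparent AUC at the 0.945 cutoff.** Simulated: 15 vs 10 patients, 12 normal predictors, logistic fits with a very small ridge so that separated data converge, 2,000 replicates for each of seven signal and correlation structures. In the middle column no combination of predictors has AUC above 0.8, so every rejection is an error.

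| Model tested | Best attainable AUC 0.8 | Pure noise (0.5) |
|---|---|---|
| Fixed marker, no selection | 3–5% | 0% |
| Best 1 of 12 by AUC | 1–12% | 0.1% |
| Best 2 | 8–25% | 0.8% |
| Best 3 | 27–40% | 5% |
| Forward selection, p<0.05 | 23–31% | 7% |
| Forward selection, AIC | 45–59% | 25% |
| All six CEUS metrics, no selection | 28–30% | 4% |
| All 12, no selection | 86–88% | 58% |

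The upper values for the best single predictor come from strongly correlated predictors. Repeat runs of the independent-predictor case, with signal in one predictor, gave 16–18% for two, 32–35% for three and 85–87% for all 12. In one set of those runs mean apparent AUC was 0.88 to 0.98, while the fitted models' mean true AUC was 0.65 to 0.71.

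The SE matters too. With a DeLong SE, a fixed marker with no selection already rejects about 12%.

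**5. Section 7.2.2.** No infusion candidate list is given. Section 1.6 notes that "the infusion method TIC does not quantify a wash-out rate", so the sets probably differ. Assume 8 infusion candidates (A, β, 3 B-mode, 3 patient) against 12 for bolus, with best attainable AUC 0.8 for both. Mean apparent AUC is then 0.87 vs 0.88 with the best two predictors, and 0.93 vs 0.98 with all entered.

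**6. Does cross-validation repair the level?** At the 0.945 cutoff with equal spread in both groups, repeating forward AUC selection inside every leave-pair-out fold gave 0.3–4.4% (maximum one predictor) and 1.2–3.1% (maximum two or three). Two pre-specified predictors gave 2.6–3.8%. Unequal spread weakens this. If the non-clear-cell SD is two or three times the clear-cell SD (assumed ratios), a fixed marker at true AUC 0.8 rejects about 7% or 8.5% at 15/10, and about 12% or 16% at 19/6.

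**The case against.** The strongest reply is that the inflation depends on choices the plan leaves open. That stands. A reader might infer from the table that the plan's error rate is near 87%. The documents do not support this: they call for selection, and the rows with all 12 or all six CEUS metrics involve none. With one selected predictor the level may even hold. A reader might also infer that the test would often pass a model with no signal. For one or two selected predictors it would not, since rejection under pure noise is below 1%. But a 5% test must hold over the whole null, including an AUC of 0.8, and the plan's wording about multiple parameters and a single score makes models of two or more predictors the natural reading.

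A second reply is that this is a 25-patient, single-arm study whose endpoint (Section 2.3) is to identify the best-predicting metrics, with no treatment decision tied to the test. That is fair, and it is why exploratory labelling leads the fix. The plan does not apply that label here. It does make such a concession for the staging aim (Section 7.1.2.2).

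A third inference would be that the comparisons in Section 7.2.2, including "We will conduct similar tests comparing the AUC based on the combined model to those based on bolus and infusion multiparametric scores separately", are materially tilted towards the larger candidate set. This is possible, but the gap is about 0.01 for two-predictor models and rests on an assumed candidate list.

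Finally, a null-SE cutoff might be thought to restore an exact 5%. It does not: the cutoff depends on which group is called positive, and the level drifts when spreads differ. That is plausible here because the non-clear-cell group mixes subtypes, which Section 1.3 says differ in vascularity.

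**Conclusion.** The concern holds. As written, the primary test applies a one-sided 5% criterion to the apparent AUC of a model selected and fitted in the same 25 patients, with no correction, so its level is not assured. At the boundary, false rejection runs from about 1–12% for one selected predictor to 8–25% for two and 27–40% for three. The 86–88% for all 12 entered is an upper-end case. These figures assume normal predictors, a 15/10 split, the seven structures tried and a Hanley-McNeil SE at 0.8. The fault is not specific to selecting on AUC, since selection by p-value or AIC shows it as well. The AUCs in Section 7.2.2 are optimistic for the same reason; the size of any tilt between bolus and infusion is unknown.

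**What to change.** **Lead option.** In Section 7.2.1, and where Section 7.2.2 reuses it, replace the two selection sentences with one. Fix the algorithm and the maximum model size before outcome data are seen. Estimate AUC by cross-validation (for example leave-pair-out) that repeats all selection and fitting in every fold. Report that AUC with an interval labelled approximate: in the simulations, 95% intervals obtained by inverting the null-SE test covered 74–96% with nested selection or ridge. Report the apparent AUC as descriptive only and label the test of AUC above 0.8 exploratory. This fits the endpoint in Section 2.3. List the infusion candidates in Section 7.2.2.

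**If a formal test is kept.** Apply it to the cross-validated AUC of the capped, pre-stated procedure, or to one pre-specified metric, score or model with at most two predictors. The null needs careful wording: when stronger combinations existed but the selected single metric was itself at or below 0.8, rejection reached 6–13%. Use an SE at AUC 0.8, and either name clear cell as the positive group or take the larger SE. Suggested text:

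> AUC will be estimated by leave-pair-out cross-validation repeating the pre-stated selection algorithm (maximum k predictors) and all fitting. The hypothesis that no combination of the candidates has AUC above 0.8 is rejected if (AUC_cv − 0.8)/SE0 > 1.645, SE0 being the larger of the two Hanley-McNeil SEs at AUC 0.8 for the observed group sizes; the level is approximate.

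Do not cite 63.2% and 88.7% as power for this test.

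**Cost.** Plan wording and analysis programming, with no new patients or data. The reported AUC will be lower. Power at a true AUC of 0.90 is about 22–28% for a fixed marker or two pre-specified predictors at the 0.945 cutoff, less with the larger SE, and 2–27% with nested selection of one to three predictors. Pre-specifying one metric also moves the search for the best metric out of the formal test, which changes the role of the endpoint in Section 2.3.

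### The primary endpoint is filled by selecting on fitted AUC, and the plan has no rule that can conclude that no CEUS metric predicts histology

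*Combined protocol and SAP*

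**What the plan says.** Section 2.3 states the endpoint: "The primary study endpoint will be 3D CEUS generated metric(s) that best predict kidney mass diagnosis based on pathologic examination". It sets no threshold and does not say what is reported if no metric predicts.

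Section 7.2.1 builds logistic models for clear cell versus other histology from 12 candidates (Table 1): six CEUS factors, three B-mode factors and three patient factors. The AUC is estimated from the fitted models. The selection rule is "We will use model selection procedures based on optimizing AUC to identify a final model". The sentence just before it is almost identical, but lists AUC as one selection procedure among others that it does not name. Two further analyses are planned: hypothesis tests on individual coefficients, with no stated alpha or multiplicity control, and a one-sided test at 0.05 of the final model's AUC against 0.8. Neither is tied to the naming of a metric.

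Section 7.1 gives the size: "We will enroll 25 adult subjects". Section 7.1.1.1 assumes 60% clear cell, which is 15 against 10.

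**The concern.** The AUC of a fitted model carries no charge for extra terms. In 25 patients, with 12 candidates to choose from, it usually rises when a noise variable is added. A rule that maximises it will therefore tend to return CEUS metrics whether or not they relate to histology, and will seldom drop a useless one.

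What is at stake is the content of the primary endpoint. A list that appears regardless of the truth says little about whether 3D CEUS carries diagnostic information. When one metric does work, the list may not separate it from the noise selected with it. This is distinct from the level of the AUC-versus-0.8 test: correcting the reported AUC after selection leaves the same metrics in the model.

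**Working it through.** **Inputs.** From the plan: n = 25; 0.60 × 25 = 15 clear cell and 10 other; 6 + 3 + 3 = 12 candidates; AUC from the fitted model. Assumed, because the plan is silent: the search algorithm, the stopping rule and the correlation among metrics.

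**Step 1. The plan's own figures.** Section 7.1.1.1 says "The proposed sample of 25, assuming 60% clear cell legions, achieves 63.2% power to detect a difference of 0.1000", and 88.7% for 0.15, two-sided, with correlation 0.9. The binormal variance is V(A) = 0.0099·exp(−a²/2)·[(5a²+8) + (a²+8)/k]/15, with a = 1.414·Φ⁻¹(A) and k = 10/15.
- V(0.80) = 0.00949, V(0.90) = 0.00528, V(0.95) = 0.00244.
- Null SE of the difference: √(2 × 0.00949 × 0.1) = 0.0436.
- Alternative SE, √(V₁ + V₂ − 2 × 0.9 × √(V₁V₂)): 0.0450 for 0.90 and 0.0572 for 0.95.
- Power: Φ[(0.10 − 1.96 × 0.0436)/0.0450] = 62.7%, and Φ[(0.15 − 1.96 × 0.0436)/0.0572] = 87.0%.

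Both are within 2 points of the plan, which supports the 15/10 split. The plan states no figure for how often selection returns a CEUS metric, so the rest has no stated counterpart.

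**Step 2. Why the rule rarely returns nothing.** The fitted AUC is the share of the 15 × 10 = 150 pairs that the model ranks correctly. A logistic fit chooses the sign of its coefficient, so the best single noise variable starts well above 0.5: on average 0.72 for the best of 12 and 0.70 for the best of the six CEUS metrics. A forward search on this AUC therefore always takes a first step. Over 12 noise candidates it ended with about six terms and a mean AUC of 0.92.

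**Step 3. Simulated trials, 15 versus 10, no CEUS metric informative.**

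| Assumed selection rule | At least one CEUS metric in final model |
|---|---|
| Forward, fitted AUC, 12 candidates, uncorrelated metrics | 98-99% (mean about 3 of 6) |
| Same, correlation 0.8 among curve metrics | 94% |
| Same, two non-CEUS factors informative (joint AUC about 0.8) | 94% |
| Best subset, fitted AUC | at least 98.9% |
| Forward, fitted AUC, CEUS candidates only | 100% |
| Minimum gain 0.02 | 95% |
| Minimum gain 0.05 | 67-85% |
| 5-fold AUC, 12 candidates (CEUS only) | 85% (99%) |
| Leave-one-out AUC, 12 candidates (CEUS only) | 79% (80%) |
| AIC | 63-74% |
| BIC | about 45% |

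**Step 4. If the planned tests were made conditions** (again with no informative CEUS metric).
- Wald p < 0.05 in the final model: a useless CEUS metric is named in 21-27% of trials in one set of runs and 12-23% in a second, depending on the rule. For comparison, six independent tests at 0.05 give 1 − 0.95⁶ = 26.5%.
- Final model contains a CEUS metric and passes the test against 0.8 on the same data: 53% with 12 candidates, 8% with CEUS candidates only.
- Both conditions together: about 2-9%.

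**Step 5. One true metric (AUC 0.90), five noise metrics.** At least one noise metric joins the model in 87% of trials (mean 1.6), or 18-19% with a 0.05 minimum gain.

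**The case against.** The strongest reply is that the plan names no algorithm, so no single percentage belongs to this trial. That is right. A reader might infer that 99% of null trials would name a CEUS metric, but this needs a forward search on same-data AUC with uncorrelated metrics. The wash-in, wash-out, transit-time, time-to-peak and peak metrics come from the same curve and are probably correlated. The neighbouring sentence also leaves room for other criteria, but it names none and so supplies no stopping rule.

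Second, entering the model is not the same as being declared successful. The plan has coefficient tests and a test against 0.8, and a reader of all the outputs would be misled far less often (step 4). This stands as a limit on the consequence. It does not remove the defect, because the plan makes neither test a condition of the endpoint. The false naming that remains under Wald tests is ordinary unadjusted multiplicity over six metrics; the simulations show no excess beyond it.

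Third, one might infer that the primary output is a list of metrics to take into larger studies. The documents mention larger future studies only in Section 7.1.2.2, for the staging objective.

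Fourth, one might infer that optimism correction cannot help at all. It helps somewhat if the corrected AUC drives the selection: the figure falls to 79-85% with 12 candidates.

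Finally, an endpoint worded as what predicts best always has a winner. That is so, and it is why the endpoint needs a rule for when the winner is no better than chance.

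**Conclusion.** The concern holds in conditional form. As written, the primary endpoint is chosen by a criterion that favours adding noise, and the plan has no stated route to a negative result. With forward selection on fitted AUC, about 94-100% of trials without an informative CEUS metric still put one in the final model. Under the other rules examined with 12 candidates the range is about 45% (BIC) to 95% (a minimum gain of only 0.02), so changing the selection penalty alone does not solve it.

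These figures rest on a 15/10 split, simulated predictors and selection rules that the plan does not state. They describe which metrics are retained. The documents do not support reading them as the chance that the trial claims success. The change should be made before the analysis.

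**What to change.** - Merge the two selection sentences in Section 7.2.1 into one that states the algorithm, the criterion and the stopping rule. Keep the multivariable score.
- Define the primary endpoint by a rule that can return no metric. Compute each CEUS metric's own AUC. Permute the histology labels across patients and record the largest |AUC − 0.5| of the six each time. Name a metric as predictive only if its own |AUC − 0.5| exceeds the 95th percentile of that maximum. Rank the named metrics by AUC with 95% confidence intervals, and label any other retained CEUS metric exploratory.
- State that this rule tests marginal prediction only. Tumor volume, for instance, could be named because it tracks B-mode length. Assess added value separately by comparing models with and without CEUS metrics, repeating the whole selection in each permutation or resample.
- Section 7.2.2 reuses the same model-building strategy, so the revised selection wording should apply there too.

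**Cost.** SAP wording and computing time; no extra patients or procedures. In simulation at 15 versus 10 the cut-off is an AUC of about 0.79-0.81, and a noise metric is named in about 3-5% of trials. Fewer metrics are named: a true AUC of 0.90 is named in about 91-94% of trials, 0.85 in 71-78% and 0.80 in 48-54%. A metric useful only in combination would be reported as exploratory.
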